6.4 TOXICITY CRITERIA

The following adverse event management guidelines are intended to ensure the safety of each patient while on the study. The descriptions and grading scales found in the revised NCI Common Terminology Criteria for Adverse Events (CTCAE) version 4.0 will be utilized for AE reporting. All appropriate treatment areas should have access to a copy of the CTCAE version 4.0. A copy of the CTCAE version 4.0 can be downloaded from the CTEP web site: (http://ctep.cancer.gov/protocolDevelopment/electronic_applications/ctc.htm#ctc_40).

7 NIH REPORTING REQUIREMENTS/DATA AND SAFETY MONITORING PLAN

7.1 DEFINITIONS

Please refer to definitions provided in Policy 801: Reporting Research Events found at: <https://irbo.nih.gov/confluence/pages/viewpage.action?pageId=36241835#Policies&Guidance-800Series-ComplianceandResearchEventReportingRequirements>.

7.2 OHSRP OFFICE OF COMPLIANCE AND TRAINING

7.2.1 Expedited Reporting

Please refer to the reporting requirements in Policy 801: Reporting Research Events and Policy 802 Non-Compliance Human Subjects Research found at: <https://irbo.nih.gov/confluence/pages/viewpage.action?pageId=36241835#Policies&Guidance-800Series-ComplianceandResearchEventReportingRequirements>. Note: Only IND Safety Reports that meet the definition of an unanticipated problem will need to be reported per these policies.

7.2.2 IRB Requirements for PI Reporting at Continuing Review

Please refer to the reporting requirements in Policy 801: Reporting Research Events found at: <https://irbo.nih.gov/confluence/pages/viewpage.action?pageId=36241835#Policies&Guidance-800Series-ComplianceandResearchEventReportingRequirements>.

7.3 NCI CLINICAL DIRECTOR REPORTING

Problems expeditiously reviewed by the OHSRP in the NIH eIRB system will also be reported to the NCI Clinical Director/designee; therefore, a separate submission for these reports is not necessary.

In addition to those reports, all deaths that occur within 30 days after receiving a research intervention should be reported via email unless they are due to progressive disease.

To report these deaths, please send an email describing the circumstances of the death to [contact] within one business day of learning of the death.

7.4 NIH REQUIRED DATA AND SAFETY MONITORING PLAN

7.4.1 Principal Investigator/Research Team

The clinical research team will meet on a weekly basis when patients are being actively treated on the trial to discuss each patient. Decisions about dose level enrollment and dose escalation if applicable will be made based on the toxicity data from prior patients.

All data will be collected in a timely manner and reviewed by the principal investigator or a lead associate investigator. Events meeting requirements for expedited reporting as described in section **7.2.1** will be submitted within the appropriate timelines.

The principal investigator will review adverse event and response data on each patient to ensure safety and data accuracy. The principal investigator will personally conduct or supervise the investigation and provide appropriate delegation of responsibilities to other members of the research staff.

8 SPONSOR PROTOCOL/SAFETY REPORTING

8.1 DEFINITIONS

8.1.1 Adverse Event

Any untoward medical occurrence in a patient or clinical investigation subject administered a pharmaceutical product and which does not necessarily have a causal relationship with this treatment. An adverse event (AE) can therefore be any unfavorable and unintended sign (including an abnormal laboratory finding), symptom, or disease temporally associated with the use of a medicinal (investigational) product, whether or not related to the medicinal (investigational) product (ICH E6 (R2))

8.1.2 Serious Adverse Event (SAE)

An adverse event or suspected adverse reaction is considered serious if in the view of the investigator or the sponsor, it results in any of the following:

- Death,
- A life-threatening adverse event (see section **8.1.3**)
- Inpatient hospitalization or prolongation of existing hospitalization
 - A hospitalization/admission that is pre-planned (i.e., elective or scheduled surgery arranged prior to the start of the study), a planned hospitalization for pre-existing condition, or a procedure required by the protocol, without a serious deterioration in health, is not considered a serious adverse event.
 - A hospitalization/admission that is solely driven by non-medical reasons (e.g., hospitalization for patient or subject convenience) is not considered a serious adverse event.
 - Emergency room visits or stays in observation units that do not result in admission to the hospital would not be considered a serious adverse event. The reason for seeking medical care should be evaluated for meeting one of the other serious criteria.
- Persistent or significant incapacity or substantial disruption of the ability to conduct normal life functions
- A congenital anomaly/birth defect.
- Important medical events that may not result in death, be life-threatening, or require hospitalization may be considered a serious adverse drug experience when, based upon appropriate medical judgment, they may jeopardize the patient or subject and may require medical or surgical intervention to prevent one of the outcomes listed in this definition.

8.1.3 Life-threatening

An adverse event or suspected adverse reaction is considered "life-threatening" if, in the view of either the investigator or sponsor, its occurrence places the patient or subject at immediate risk of death. It does not include an adverse event or suspected adverse reaction that, had it occurred in a more severe form, might have caused death. (21CFR312.32)

8.1.4 Severity

The severity of each Adverse Event will be assessed utilizing the CTCAE version 4.0.

8.1.5 Relationship to Study Product

All AEs will have their relationship to study product assessed using the terms: related or not related.

- Related – There is a reasonable possibility that the study product caused the adverse event. Reasonable possibility means that there is evidence to suggest a causal relationship between the study product and the adverse event.
- Not Related – There is not a reasonable possibility that the administration of the study product caused the event.

8.2 ASSESSMENT OF SAFETY EVENTS

AE information collected will include event description, date of onset, assessment of severity and relationship to study product and alternate etiology (if not related to study product), date of resolution of the event, seriousness and outcome. The assessment of severity and relationship to the study product will be done only by those with the training and authority to make a diagnosis and listed on the Form FDA 1572 as the site principal investigator or sub-investigator. AEs occurring during the collection and reporting period will be documented appropriately regardless of relationship. AEs will be followed through resolution.

SAEs will be:

- Assessed for severity and relationship to study product and alternate etiology (if not related to study product) by a licensed study physician listed on the Form FDA 1572 as the site principal investigator or sub-investigator.
- Recorded on the appropriate SAE report form, the medical record and captured in the clinical database.
- Followed through resolution by a licensed study physician listed on the Form FDA 1572 as the site principal investigator or sub-investigator.

For timeframe of recording adverse events, please refer to section 6.1. All serious adverse events recorded from the time of first investigational product administration must be reported to the sponsor with the exception of any listed in section 8.4.

8.3 REPORTING OF SERIOUS ADVERSE EVENTS

Any AE that meets protocol-defined serious criteria or meets the definition of Adverse Event of Special Interest that require expedited reporting must be submitted immediately (within 24 hours of awareness) to OSRO Safety using the CCR SAE report form. Any exceptions to the expedited reporting requirements are found in section 8.4.

All SAE reporting must include the elements described in section 8.2.

SAE reports will be submitted to the Center for Cancer Research (CCR) at: [contact] and to the CCR PI and study coordinator. CCR SAE report form

and instructions can be found at:

<https://ccrod.cancer.gov/confluence/display/CCRCRO/Forms+and+Instructions>

Following the assessment of the SAE by OSRO, other supporting documentation of the event may be requested by the OSRO Safety and should be provided as soon as possible.

8.4 WAIVER OF EXPEDITED REPORTING TO CCR

As death/hospitalization due to disease progression are part of the study objectives (efficacy-response rate), and captured as an endpoint in this study, they will not be reported in expedited manner to the sponsor. However, if there is evidence suggesting a causal relationship between the study drug and the event, report the event in an expedited manner according to section **8.3**.

8.5 SAFETY REPORTING CRITERIA TO THE PHARMACEUTICAL COLLABORATORS

The CCR Office of Regulatory Affairs will send all reports to the manufacturer as described below.

The PI or designee will report all Serious Adverse Events to the IND Manufacturer within 3 days of the Investigator(s) becoming aware of them.

Fax all SAE forms to: Lilly Global Patient Safety at [contact]

Additionally, the IND manufacturer will be provided with copies of all investigational product-related reports submitted to regulatory authorities.

8.6 REPORTING PREGNANCY

All required pregnancy reports/follow-up to OSRO will be submitted to:

[contact] and to the CCR PI and study coordinator. Forms and instructions can be found here:

<https://ccrod.cancer.gov/confluence/display/CCRCRO/Forms+and+Instructions>

8.6.1 Maternal exposure

If a patient becomes pregnant during the course of the study, the study treatment should be discontinued immediately, and the pregnancy reported to the Sponsor no later than 24 hours of when the Investigator becomes aware of it. The Investigator should notify the Sponsor no later than 24 hours of when the outcome of the Pregnancy become known,

Pregnancy itself is not regarded as an SAE. However, congenital abnormalities or birth defects and spontaneous miscarriages that meet serious criteria (section **8.1.2**) should be reported as SAEs.

The outcome of all pregnancies should be followed up and documented.

8.6.2 Paternal exposure

Male patients should refrain from fathering a child or donating sperm during the study and for at least 7 days after the last dose of baricitinib.

Pregnancy of the patient's partner is not considered to be an AE. The outcome of all pregnancies occurring from the date of the first dose until 28 days after the last dose should, if possible, be followed up and documented. Pregnant partners may be offered the opportunity to participate in an institutional pregnancy registry protocol (e.g., the NIH IRP pregnancy registry study) to provide data about the outcome of the pregnancy for safety reporting purposes.

8.7 REGULATORY REPORTING FOR STUDIES CONDUCTED UNDER CCR-SPONSORED IND

Following notification from the investigator, CCR, the IND sponsor, will report any suspected adverse reaction that is both serious and unexpected. CCR will report an AE as a suspected adverse reaction only if there is evidence to suggest a causal relationship between the study product and the adverse event. CCR will notify FDA and all participating investigators (i.e., all investigators to whom the sponsor is providing drug under its INDs or under any investigator's IND) in an IND safety report of potential serious risks from clinical trials or any other source, as soon as possible, in accordance to 21 CFR Part 312.32.

All serious events will be reported to the FDA at least annually in a summary format.

8.8 SPONSOR PROTOCOL DEVIATION REPORTING

A Protocol Deviation is defined as any non-compliance with the clinical trial Protocol, Manual of Operational Procedures (MOP) and other Sponsor approved study related documents, GCP, or protocol-specific procedural requirements on the part of the participant, the Investigator, or the study site staff inclusive of site personnel performing procedures or providing services in support of the clinical trial.

It is the responsibility of the study Staff to document any protocol deviation identified by the Staff or the site Monitor in the CCR Protocol Deviation Tracking System (PDTS) online application. The entries into the PDTS online application should be timely, complete, and maintained per CCR PDTS user requirements.

In addition, any deviation to the protocol should be documented in the participant's source records and reported to the reviewing IRB per their guidelines. OSRO required protocol deviation reporting is consistent with E6(R2) GCP: Integrated Addendum to ICH E6(R1): 4.5 Compliance with Protocol; 5.18.3 (a), and 5.20 Noncompliance; and ICH E3 16.2.2 Protocol deviations.

9 CLINICAL MONITORING

Clinical site monitoring is conducted to ensure:

- that the rights of the participants are protected;
- that the study is implemented per the approved protocol, Good Clinical Practice and standard operating procedures; and,
- the quality and integrity of study data and data collection methods are maintained.

Monitoring for this study will be performed by NCI CCR Office of Sponsor and Regulatory Oversight (OSRO) Sponsor and Regulatory Oversight Support (SROS) Services contractor. Clinical site monitoring activities will be based on OSRO standards, FDA Guidance E6(R2) Good Clinical Practice: Integrated Addendum to ICH E6(R1) March 2018, and applicable regulatory requirements.

Details of clinical site monitoring will be documented in a Clinical Monitoring Plan (CMP) developed by OSRO. CMPs will be protocol-specific, risk-based and tailored to address human subject protections and integrity of the study data. OSRO will determine the intensity and frequency of monitoring based on several factors, including study type, phase, risk, complexity, expected enrollment rate, and any unique attributes of the study and the site. The Sponsor will conduct a periodic review of the CMP to confirm the plan's continued appropriateness. A change

to the protocol, significant or pervasive non-compliance with GCP, or the protocol may trigger CMP updates.

OSRO SROS Monitoring visits and related activities will be conducted throughout the life cycle of each protocol. The first activity is before the study starts to conduct a Site Assessment Visit (SAV) (as warranted), followed by a Site Initiation Visit (SIV), Interim Monitoring Visit(s) (IMVs), and a study Close-Out Visit (COV).

Some monitoring activities may be performed remotely, while others will occur at the study site(s). Monitoring visit reports will describe visit activities, observations, and associated action items or follow-up required for resolution of any issues, discrepancies, or deviations. Monitoring reports will be distributed to the study PI, NCI CCR QA, CCR Protocol Support Office, coordinating center (if applicable), and the Sponsor regulatory file.

The site Monitor will inform the study team of any deviations observed during monitoring visits. If unresolved, the Monitor will request that the site Staff enter the deviations in the CCR Protocol Deviation Tracking System (PDTS) for deviation reporting to the Sponsor and as applicable per institutional and IRB guidance.

10 STATISTICAL CONSIDERATIONS

The primary objectives of the study are to determine the tolerability and efficacy of baricitinib in patients with steroid-refractory cGVHD. The primary efficacy objective is to treat a total of 21 patients in either cohort 1 or cohort 2 in order to have 80% power to detect a response rate consistent with 30% and ruling out 10%, with a one-sided significance level of 0.10.

Patients will first be enrolled onto cohort 1, and in an initial futility analysis, if 0 of the first 7 patients enrolled in cohort 1 have responded, then subsequent patients will be accrued to cohort 2, starting treatment at the higher dose (4mg daily). If 1 or more of the initial 7 patients treated in cohort 1 has a response, then a total of 21 evaluable patients will be treated in cohort 1.

If patients are enrolled onto cohort 2, and if 0 of the first 7 patients enrolled in cohort 2 have responded, then no further patients will be accrued onto the trial. On the other hand, if 1 or more of the initial 7 evaluable patients enrolled in cohort 2 have responded then a total of 21 evaluable patients will be treated in cohort 2.

As an early stopping rule for safety, if 2/3 or greater patients at any given dose level experiences a dose limiting toxicity requiring dose reduction or discontinuation, that dose will not be subsequently used. Accrual will continue at a lower dose level with no further dose escalation, unless this occurs at the lowest dose level, at which time accrual to the study will be stopped.

If patients are enrolled in both cohort 1 and cohort 2, then up to 28 evaluable patients may be required (either 21 in cohort 1 or 7 in cohort 1 and 21 in cohort 2). In order to allow for a small number of inevaluable patients, the accrual ceiling will be set at 31. It is anticipated that 8-12 patients may be enrolled onto this protocol per year; thus, 2 to 4 years may be required to accrue up to 31 patients.

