Neutrophils $< 1.0 \times 10^9/L$, platelets $< 50 \times 10^9/L$, creatinine ≥ 1.5 times the upper limit of normal **or** estimated creatinine clearance $< 50 \text{ mL/min/1.73m}^2$ (Cockcroft-Gault formula), serum aspartate aminotransferase or alanine aminotransferase concentration $> 3 \times \text{ULN}$ or total bilirubin $\geq 1.5 \times \text{ULN}$

Progressive malignancy, uncontrolled infection or any major organ dysfunction as defined by the protocol

Design:

This is a Phase 1/2 trial to determine the safety and efficacy of baricitinib in patients with cGVHD that is refractory to steroids.

Patients will initially be treated with baricitinib at 2mg daily for 12 weeks. If the response at 12 weeks is a CR and there has not been a DLT, the dose will remain at 2mg daily for an additional 12 weeks, with the primary response assessment at 24 weeks of total treatment. If the response is a PR or stable disease, the dose will be increased to 4mg daily for an additional 12 weeks, with the primary response assessment at 24 weeks of total treatment. If there is progression of disease at any time within the first 12 weeks, the dose can be increased to 4mg daily at that time, and patients will continue for a total of 24 weeks of treatment. Patients will have the option to continue baricitinib for an additional 6 months as tolerated if they have stable or responding disease.

The co-primary endpoint of safety will be determined by rate, severity, and duration of adverse events based on CTCAE v4 criteria. Assessment for DLTs will occur every 2 weeks during the first 4 weeks of each dose level. Safety monitoring will occur every 4 weeks thereafter.

The co-primary endpoint of efficacy will be defined as rate of overall response at 24 weeks per NIH consensus criteria (CR or PR).

Peripheral blood samples will be collected prior to treatment, at 2 weeks, at 12 weeks and every 12 weeks thereafter to evaluate cytokine and cellular profiles, STAT phosphorylation, candidate chronic GVHD biomarkers. Pharmacokinetic studies will also be performed at each dose level.

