In an initial futility analysis, if 0 of the first 7 patients enrolled in cohort 1 have responded at 12 weeks, then a 2nd cohort of patients will be accrued to start treatment at the higher dose (4mg daily). Otherwise, if 1 or more of the first 7 patients respond in cohort 1, then 21 evaluable patients will be treated in cohort 1. Similarly, if the second cohort is used, and if 0 of the 7 patients enrolled in this second cohort have responded at 12 weeks, then no further patients will be accrued. Otherwise, if 1 or more of the first 7 patients respond in cohort 2, then 21 evaluable patients will be treated in cohort 2.

A total of 21 evaluable patients will be enrolled in either cohort 1 or 2 as appropriate, in order to have 80% power to detect a response rate consistent with 30% and ruling out 10%, with a one-sided significance level of 0.10 for the cohort. As an early stopping rule for safety, if 2/3 or greater patients at any given dose level experiences a dose limiting toxicity requiring dose reduction or discontinuation, that dose will not be subsequently used and no further dose escalation will take place.

TABLE OF CONTENTS

PRÉCIS	2
TABLE OF CONTENTS	4
STATEMENT OF COMPLIANCE	7
1 INTRODUCTION	7
1.1 Study Objectives	7
1.2 Background and Rationale	7
2 ELIGIBILITY ASSESSMENT AND ENROLLMENT	12
2.1 Eligibility Criteria	12
2.2 Screening Evaluation	14
2.3 Participant Registration and Status Update Procedures	14
2.4 Baseline Evaluation	15
3 STUDY IMPLEMENTATION	16
3.1 Study Design	16
3.2 Drug Administration	19
3.3 Dose Modifications	19
3.4 Questionnaires	20
3.5 Follow-up	20
3.6 Telehealth	21
3.7 Study Calendar	22
3.8 Cost and Compensation	26
3.9 Criteria for Removal from Protocol Therapy and Off Study Criteria	26
4 CONCOMITANT MEDICATIONS/MEASURES	27
4.1 Concomitant Corticosteroid Therapy and Tapering Guideline	27
4.2 Other Treatments for cGVHD	27
4.3 Other Allowed Concomitant Therapy	28
4.4 Prohibited Concomitant Therapy	28
5 CORRELATIVE STUDIES FOR RESEARCH	28
5.1 Biospecimen Collection	28
5.2 Sample Storage, Tracking and Disposition	30
6 DATA COLLECTION AND EVALUATION	32
6.1 Data Collection	32
6.2 Data sharing plans	33

6.3	Response Criteria.....	33
6.4	Toxicity Criteria.....	36
7	NIH REPORTING REQUIREMENTS/DATA AND SAFETY MONITORING PLAN...36	
7.1	Definitions	36
7.2	OHSRP Office of Compliance and Training.....	36
7.3	NCI Clinical Director Reporting	37
7.4	NIH Required Data and Safety Monitoring Plan.....	37
8	SPONSOR SAFETY REPORTING.....	37

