3 STUDY IMPLEMENTATION

3.1 STUDY DESIGN

This is a phase 1/2 single arm study to evaluate the safety and efficacy of baricitinib at doses of 2mg-4mg in patients with cGVHD after SCT. Doses of 0.5mg-20mg have been studied in patients with autoimmune diseases and have demonstrated a good safety profile (Baricitinib Investigator's Brochure, Eli Lilly and Company). Based on studies in patients with RA, there seems to be a plateau efficacy response at doses above 4mg daily, and it is the 4mg daily dose that was taken to the Phase 3 studies. In addition, in anecdotal experience with JAK inhibitors in patients with GVHD, low doses appear to be sufficient for response.

Patients will be enrolled in up to 2 sequential cohorts of up to 21 patients.

The first cohort of patients will be treated with baricitinib starting at a dose of 2mg daily for 12 weeks. For safety purposes, patients who experience a DLT within the first 4 weeks will be able to restart at 1mg daily, and will continue at this dose as tolerated (see Section 3.1.1). If they experience a DLT at this dose, they will be taken off treatment. Regarding efficacy, patients who have a complete response (CR) on 2mg daily at 12 weeks will continue the same dose until the 24 week time point for the primary efficacy endpoint. For patients who have a partial response (PR) or unchanged disease at 12 weeks, the dose will be increased to 4mg daily until the primary efficacy endpoint response assessment at 24 weeks. Following any dose increase to 4mg, patients who experience a DLT within the first 4 weeks will have a dose reduction back to 2mg daily. For patients who experience cGVHD progression at any time within the first 12 weeks on 2mg daily, the dose can be increased to 4mg daily up until the primary efficacy endpoint response assessment at 24 weeks, unless they experience a DLT. Prior to the 12 week response assessment, an initial response assessment will occur at 6 weeks, but there will be no dose changes unless there has been progression or toxicities, as outlined. If at least 1 patient in the first cohort has a PR or CR, the remainder of the study will follow the initial schema as above, and 21 evaluable patients will be treated as part of cohort 1. After the primary response assessment, patients who have unchanged or responding disease will have the option to continue baricitinib for an additional 6 months as tolerated.

[figure not shown]
[figure not shown]

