If no patients among the first 7 achieve a CR or PR on 2mg daily at the 12 week response assessment in the first cohort of patients, the second cohort will be enrolled starting at 4mg daily if no safety issues have arisen, with the same parameters for DLT monitoring. Similarly, if 0 of the first 7 treated in cohort 2 have a response, then no further patients will be treated in cohort 2.

If there is at least one patient with a response in the first 7 patients treated on cohort 2, then 21 evaluable patients will be treated in cohort 2.

Concurrent topical and ancillary treatments for cGVHD are allowed per standards of care and will be recorded (see Section 4). Other systemic immune suppression must stay stable or be tapered (systemic immunosuppression taper should be attempted no earlier than after 4 weeks on study), throughout the treatment with baricitinib (with up to 2 steroid pulses allowed for disease stabilization per Section 4.1).

Patients who discontinue therapy for any reason will be followed for up to 24 months after discontinuing baricitinib as indicated in section 3.5.

Peripheral blood samples will be collected prior to treatment, at 2 weeks, at 12 weeks and every 12 weeks thereafter to evaluate cytokine and cellular profiles, STAT phosphorylation, candidate chronic GVHD biomarkers. Pharmacokinetic studies will also be performed at each dose level on day 1 and after 15 days of treatment (Section 5.1.3).

*If ≥ 1 response in cohort 1, 2nd cohort will use identical schema as cohort 1

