3.1.1.1 Dose Escalation

This study will include an intra-patient dose escalation. The starting dose of baricitinib will be 2mg PO daily, a dose that has been well tolerated in previous studies of patients with autoimmune diseases. The first 7 subjects will be treated for a total of 12 weeks at this dose, unless they demonstrate cGVHD progression prior to this, at which time they will increase the dose to 4mg. If patients have a CR, they will continue at this dose until the primary efficacy endpoint. If patients have a PR or unchanged disease (see Section 6.3), the dose will increase to 4mg until the primary efficacy endpoint evaluation takes place at 24 weeks, unless they experience a DLT. If at least 1 patient of the first 7 in cohort 1 has a response, subjects will follow the original dose escalation schema. If 0 of these first 7 patients have a response, then patients will begin to be enrolled onto cohort 2, and will be started at the 4mg PO daily dose initially, unless they experience a DLT, at which time they will decrease the dose to 2mg.

As an early stopping rule for safety, if 2/3 or greater patients at any given dose level experiences a dose limiting toxicity requiring dose reduction or discontinuation, that dose will not be subsequently used.

Intra-patient Dose Escalation Schedule	
Dose Level	Dose of IND Agent
Level -1	1mg
Level 1	2mg
Level 2	4mg

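### The stated 80% power for 21 patients ignores the stop at 0 of the first 7; with it, per-cohort power is 76.7%, and no success cut-off is written

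*Combined protocol and SAP*

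**What the plan says.** Section 10 (Statistical Considerations) plans 21 patients in cohort 1 or cohort 2 to have "80% power to detect a response rate consistent with 30% and ruling out 10%, with a one-sided significance level of 0.10". The Précis repeats the statement and attaches it to a single cohort: "80% power to detect a response rate consistent with 30% and ruling out 10%, with a one-sided significance level of 0.10 for the cohort".

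Both places prescribe an early look. In Section 10, "if 0 of the first 7 patients enrolled in cohort 1 have responded, then subsequent patients will be accrued to cohort 2". The same rule applies to cohort 2, where 0 of 7 ends accrual to the trial. If at least one of the 7 responds, the cohort continues to 21 evaluable patients.

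The final endpoint is set at 24 weeks: "The co-primary endpoint of efficacy will be defined as rate of overall response at 24 weeks".

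The look itself is worded in several ways:

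- Précis: "if 0 of the first 7 patients enrolled in cohort 1 have responded at 12 weeks".
- Section 3.1: "If no patients among the first 7 achieve a CR or PR on 2mg daily at the 12 week response assessment". Just before that, the continuation rule reads "If at least 1 patient in the first cohort has a PR or CR, the remainder of the study will follow the initial schema", with no limit to the first 7 and no time point.
- Section 3.1.1.1: "If 0 of these first 7 patients have a response, then patients will begin to be enrolled onto cohort 2", with no time point in the rule.
- Section 10: no time point, and the seven are variously called enrolled, treated and evaluable.

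The plan does not give the number of responses that counts as success. It does not name a two-stage design or say whether the 80% allows for the stop.

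**The concern.** A futility stop can only lower the power of a fixed final test, because some cohorts that would have reached the success count are closed first. A sample size of 21 that just reaches 80% without the stop must therefore fall below 80% with it. The sponsor would then be relying on an operating characteristic that the per-cohort design does not have.

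The missing cut-off adds to this. At 21 patients, 4 and 5 responses lie on opposite sides of the plan's own 0.10 limit. A reader has to infer the decision rule for a co-primary endpoint from the alpha and power figures.

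**Working it through.** **Inputs** (Section 10 and Précis): null rate p0 = 0.10, alternative p1 = 0.30, one-sided alpha at most 0.10, first look at 7 patients with a stop at 0 responses, final size 21. The cut-off r is not given and must be inferred.

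**1. Reproduce the stated 80%.** Single stage, exact binomial, P(X ≥ r) with X ~ Bin(21, p):

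| r | alpha (p = 0.10) | power (p = 0.30) |
|---|---|---|
| 4 | 0.1520 | 0.9144 |
| 5 | 0.0522 | 0.8016 |

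At least 5 of 21 is the smallest cut-off within 0.10, and it gives 80.2%. The stated figure is therefore the single-stage power.

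**2. Add the prescribed stop.** With x the number of responses among the first 7, the probability of success is

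sum over x = 1 to 7 of Bin(x; 7, p) × P(Bin(14, p) ≥ 5 − x).

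At p = 0.30:

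| x | Bin(x; 7, 0.3) | P(Bin(14, 0.3) ≥ 5 − x) | product |
|---|---|---|---|
| 1 | 0.2471 | 0.6448 | 0.1593 |
| 2 | 0.3177 | 0.8392 | 0.2666 |
| 3 | 0.2269 | 0.9525 | 0.2161 |
| 4 | 0.0972 | 0.9932 | 0.0966 |
| 5 to 7 | 0.0288 | 1 | 0.0288 |

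The sum is 0.7674. The same sum at p = 0.10 is 0.0477.

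**3. Check the difference.** The loss is the chance of 0 of 7 times the chance of at least 5 in the other 14: 0.7^7 × 0.4158 = 0.0824 × 0.4158 = 0.0342, which equals 0.8016 − 0.7674.

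**4. Does a lower cut-off help?** At least 4 of 21 with the stop gives power 0.8613 but alpha 0.1309, above the limit.

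**5. Other bases for a power figure** (at least 5 of 21, with the stop):

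- Conditional on passing the look: power 0.7674 / (1 − 0.7^7) = 0.836; alpha 0.0477 / (1 − 0.9^7) = 0.092.
- Success in either cohort, both at the same true rate: power 0.7674 × (1 + 0.7^7) = 0.831; alpha 0.0477 × (1 + 0.9^7) = 0.071.

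**6. Look at 12 weeks, endpoint at 24 weeks.** Step 2 treats the two responses as the same. The documents give no 12-week rate, so the following is an assumed range. Let s be the share of 24-week responders who already respond at week 12, and t the share of 24-week non-responders who count as responders at week 12. Each term of the sum (now from x = 0) is Bin(x; 7, 0.3) × [1 − (1 − s)^x (1 − t)^(7−x)] × P(Bin(14, 0.3) ≥ 5 − x).

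| s | t | power |
|---|---|---|
| 1 | 0 | 76.7% |
| 0.8 | 0 | 72.3% |
| 0.6 | 0 | 64.4% |
| 0.5 | 0 | 58.7% |
| 1 | 0.1 | 78.5% |
| 1 | 0.2 | 79.4% |

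Every case is below 80%.

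**7. Other sizes with the same 0 of 7 look** (step 2 assumption):

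| rule | alpha | power |
|---|---|---|
| at least 4 of 18 | 0.089 | 80.0% |
| at least 5 of 22 | 0.056 | 79.6% |
| at least 5 of 23 | 0.065 | 81.9% |

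**The case against.** The strongest reply is that the sentence is not false on its face. It ties 80% to treating 21 patients, and for 21 treated patients the exact figure is 80.2%. Conditional on passing the look it is 83.6%, and across both cohorts at equal 30% rates it is 83.1%. Only the unconditional per-cohort reading falls short, and then by about 3 points with alpha well inside its limit. The wording does not exclude the conditional reading.

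That reply fixes the size of the problem but does not remove it. The Précis attaches the figure to the cohort. The single-stage figure leaves out a stop that the same sections prescribe. The conditional and either-cohort figures are not 80%, and the plan states neither. In cohort 2 there is no second chance to offset the loss.

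It is also fair to say that 76.7% depends on response at the look and at 24 weeks coinciding. The true figure could be nearer 80% if some patients respond at week 12 and not at week 24. It could be well below if responses come late. In cohort 1, patients with a partial response or unchanged disease have a dose change between the two time points, so late responses are plausible. The assumption must be written next to the number.

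On the wording of the look, part of the objection stands. The limit to the first 7 that is missing from one sentence of Section 3.1 is supplied shortly afterwards. Section 3.1.1.1 mentions 12 weeks of treatment earlier in the same paragraph. The evaluability definition in Section 6.3.1 concerns the 6-month endpoint, so it leaves evaluable at 12 weeks undefined and does not contradict the look. These are clarifications, secondary to the power figure.

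**Conclusion.** The point holds. The 80% is the power of a single-stage rule of at least 5 of 21. The per-cohort design as written, with the stop at 0 of the first 7, has power 76.7% and alpha 0.048. The shortfall from 80% is 3.3 points.

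This rests on two assumptions. The cut-off is inferred as the smallest with exact alpha at or below 0.10, and a response at the look is taken to be a response at 24 weeks. Under the assumed departures from the second, power runs from 58.7% to 79.4%.

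The consequence is limited. Type I error is not inflated, and in cohort 1 the stop moves accrual to cohort 2. It is still worth correcting, because a stated design property and the success threshold of a co-primary endpoint both depend on it.

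**What to change.** In the Précis and Section 10, replace the 80% statement with text such as:

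> Success is at least 5 responses (CR or PR) at 24 weeks among 21 evaluable patients in the cohort. With the stop at 0 of the first 7, exact one-sided alpha is 0.048 and power is 77% for 10% versus 30%, if response at the look and at 24 weeks coincide.

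If the sponsor meant power conditional on passing the look, the text should say so and give alpha 0.092 and power 84%.

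Second, use one wording for the look in the Précis, Sections 3.1 and 3.1.1.1, and Section 10. It should give the time point, whether responses after a dose change count, and whether the seven are enrolled, treated or evaluable. If evaluable, it should define the term at 12 weeks.

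The cost is protocol wording only, with no added patients; the stated power falls from 80% to 77%. If the sponsor prefers to keep 80%, at least 5 of 23 gives 81.9% under the same coincidence assumption (about 77% if only 80% of 24-week responders have responded by week 12 and no one else has). That needs two more evaluable patients in the cohort, so at most 7 + 23 = 30 evaluable instead of 7 + 21 = 28. Against the accrual ceiling of 31, this leaves one place for an inevaluable patient.
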